This will be the first large scale study of the pathway to diagnosis in primary care, giving an unprecedented detailed account of the symptoms, numbers of visits, diagnostic tests, misdiagnosis and overall presentation of children with new onset T1D. Results will also build on research (the EDDY study: Early Diagnosis of Diabetes in Youth) currently being undertaken by the applicant and two of the co-applicants funded through the National Institute for Social Care and Health Research for Patient and Public Benefit scheme. EDDY is a feasibility study designed around King's (12) successful intervention in Australia, with the aim of designing and delivering interventions for parents, GPs and practice nurses, to raise awareness of the symptoms of T1D to prevent presentation in DKA at diagnosis. This study will identify whether there are additional opportunities to promote an earlier diagnosis, which may require interventions different or additional to those undergoing preliminary evaluation in EDDY.

Research questions

- 1. Are there factors (number and reasons for consultations, socio-demographic factors, past medical history), or combinations of factors, that are associated with a new diagnosis of T1D, as compared to children presenting with other acute conditions in the 12 months before diagnosis?
- 2. Are there differences in the patient pathway (12 month period before diagnosis), as recorded in their medical records, between patients presenting with newly diagnosed T1D who experience DKA, and those who do not experience DKA around the time of diagnosis?

5 Study objective(s)

The ultimate aim of this research is to promote earlier diagnosis of type 1 diabetes (T1D) in childhood to reduce the risk of DKA at presentation by better understanding the pathway to diagnosis through analysis of the number and reason for appointments of the child with their Primary Care Team before diagnosis and any tests conducted at these times.

Primary objective

 To investigate if there are any factors that are associated with a new diagnosis of T1D in childhood, compared to a matched group of controls without T1D, during the 12 months preceding diagnosis.

Secondary objectives

 To investigate if there are any risks associated within the patient pathway in the 12 months preceding diagnosis between children who presented in DKA or not in DKA at diagnosis.

6 Study design

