them into those who presented with or without DKA at diagnosis. Extrapolations from the Welsh data suggest that there will be approximately 3500 children diagnosed with T1D in these years, with at least 90 children who presented in DKA. The SAIL research analyst will link these data with the GP dataset from the SAIL databank using first and last name, gender, date of birth, date of diagnosis, DKA status, GP and postcode (NHS number is not recorded in the Brecon Group Register). The dataset generated from this process will be anonymised using an ALF, ensuring the researchers do not have access to any personal identifiable data (e.g. age at diagnosis in DKA will be calculated using date of birth and date of diagnosis and then date of birth will be discarded). In addition, a cohort of controls presenting to their GP with acute illness but who do not have T1D will be identified from SAIL at the ratio of 3:1. This cohort will be matched to the T1D cohort by age, gender and GP practice. The resulting dataset therefore will contain all GP consultation records in the 12 months prior to diagnosis for children diagnosed with T1D, those diagnosed in DKA and a matched cohort of children without T1D. The cohort of children without T1D will be assigned a matched date to act as the time point for consultations in the previous 12 months. Children presenting with T1D (in or not in DKA at diagnosis) who cannot be matched (due to their GP data not being available in SAIL) will be compared to children presenting with T1D matched to SAIL, and any differences will be quantified.

Inclusion criteria

- All children 15yrs and under diagnosed with T1D between 1st January 2000 and 31st
 December 2015 and listed in the Brecon Group database.
- Matched controls, for those above, from the SAIL databank

Exclusion criteria

- All children over 15yrs old diagnosed with T1D
- All children diagnosed before 1st January 2000 and after 31st December 2015

9 Outcome measures

There are no primary or secondary end points for this study

10 Recruitment

This study is using routinely collected data and therefore will not be actively recruiting participants

Informed consent

Informed consent will not be sought from participants as all data is anonymised and is provided from existing datasets.

Randomisation/registration and unblinding

This is a case control study and therefore no participants will be randomised.

Screening logs

Not applicable

11 Withdrawal & loss to follow-up

Not applicable

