
12 Intervention

Not applicable

13 Adverse Events

Adverse Event (AE):

There are no expected AEs/SAEs.

Related Adverse Event/Serious Adverse Events:

There are no expected AEs/SAEs that could be related to the study. Therefore, there will be no formal process in place to collect AEs or SAEs for this study.

Adverse Event (AE):

Not applicable

Causality

Reporting procedures

Not applicable

14 Study procedures

This study will link two existing datasets, the Brecon Group (Welsh Paediatric Diabetes Interest Group) Register and GP records within the SAIL databank, to provide a unique and contemporary dataset of all children in Wales diagnosed with T1D in the 16 year period between 1st January 2000 and 31st December 2015 (approximately 3500), with details of the number and nature of any GP consultations they may have had in the 12 months before diagnosis. In addition, a cohort of children without T1D but matched for age, gender, location, socioeconomic class, GP and another acute illness (e.g. infection) will be identified to explore the specificity and predictive potential of variables related to development of T1D.

The first stage of the study will involve identifying all children (i.e. those under 15yrs of age) diagnosed with T1D from 1st January 2000 to 31st December 2015 in the Brecon Group Register and categorising them into those who presented with or without DKA at diagnosis. Extrapolations from the Welsh data suggest that there will be approximately 3500 children diagnosed with T1D in these years, with at least 700 children who presented in DKA. The SAIL research analyst will link these data with the GP dataset from the SAIL databank using:-

- First and last name
- Gender
- Date of birth
- Date of diagnosis
- DKA status
- GP practice
- Postcode (NHS number is not recorded in the Brecon Group Register).

The dataset generated from this process will be anonymised using an ALF, ensuring the researchers do not have access to any personal identifiable data (e.g. age at diagnosis in DKA will be calculated using date of birth and date of diagnosis and then date of birth will be discarded). In addition, a cohort of controls presenting to their GP with acute illness but who do not have T1D will be identified from SAIL at the ratio of 3:1. This cohort will be matched to the T1D cohort by:-

- Age
- Gender
- GP practice

The SAIL analyst will extract the following information:-

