- All GP consultation records in the 12 months prior to diagnosis for children diagnosed with T1D
- All GP consultation records of the matched cohort of children without T1D. (This cohort will be matched on the date they presented to their GP with an acute illness. This will act as the time point for consultations in the previous 12 months.)

Within the consultation records variables will include:-

- Symptom details
- Diagnoses
- Tests undertaken
- Medication prescribed
- Co-morbidities

Demographic factors collected

- Children
 - Age at diagnosis
 - Gender
 - Deprivation quintile (based on postcode)
 - GP practices
 - List size
 - Number of GPs within the practice.

Initial analysis of the dataset will assess and explore the read codes attached to each GP consultation in the 12 months before diagnosis. The researchers will define the read codes and explore mechanisms for grouping symptoms to allow for meaningful clinical interpretation. Each patient's prodrome (the 12 months before diagnosis) will be assessed by analysing the number of GP visits, symptoms, diagnoses, tests undertaken and treatments given.

15 Statistical considerations

Randomisation

Not applicable

Sample size

As the primary purpose of this study is to seek an earlier diagnosis of T1D, the study is powered for the case-control study. Assuming a medium effect size (OR=1.5), a moderately low prevalence rate of the risk factor 30% in the control group, matching 3 controls per case and using a two sided 5% alpha and 80% power, we will require 322 children with T1D. If a total of around 390 children diagnosed with T1D were identified between 2010 and 2012 this would give the study over 90% power. A secondary aim of the study is to explore the risks associated with presenting in DKA (or not). Given that approximately 23% of children diagnosed with T1D are in DKA at diagnosis then we have 90 children in DKA and 300 not in DKA, we will not be powered to observe any small to medium effect sizes for any risk factors. This analysis will be exploratory in nature.

16 Analysis

Main analysis

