The two groups will be described using summary statistics (N (%), mean (sd), median (inter-quartile range)) for the explanatory variables identified as described above. Predictors of presenting in DKA at diagnosis (using the explanatory variables identified) will be examined using a two-level logistic regression model (children within practice). Where numbers allow, variation in DKA will be accounted and corrected for at the level of general practice. Associations between the prodromes for children presenting in DKA will be examined firstly at the univariable level and significant predictors (with a P-value <0.10) retained for the multivariable model. Odds ratios (ORs) will be estimated together with 95% confidence intervals (CIs).

The quality of the matching will be examined by describing the case-mix (with respect to age, gender, co-morbidites and practice factors) of the case (T1D) and control (general population of children) groups. The two groups will be also be described to examine any differences in prevalence of presentation of such symptoms, GP visits, tests and medications in primary care. A similar analysis will be used as in the T1D analysis only using a conditional logistic regression model to account for the non-independent observation created by matching, and results again presented as ORs alongside 95% CIs.

Data storage & retention

All data will be kept for 15 years in line with Cardiff University's Research Governance Framework Regulations for clinical research. This data will be stored confidentially on password protected servers maintained on the Cardiff University Network.

17 Study closure

The end of the study will be considered as the date of the submission of the final report.

18 Regulatory issues

Ethical and research governance approval

The study will be conducted in accordance with the recommendations for physicians involved in research on human participants adopted by the 18th World Medical Assembly, Helsinki 1964 and later revisions. The study will be submitted to an NHS Research Ethics Committee (NHS REC) for approval. This is consistent with the requirements of Cardiff University who will be requested to act as the study sponsor.

Consent

Informed consent will not be sought from participants, as the data being used is anonymised and patients who contribute to the Brecon Group register provide consent for their data to be used for research purposes.

Confidentiality

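### Controls must have attended a GP with acute illness, cases need not, and section 16 labels those controls general population: ORs for visit counts and infection-type codes are biased downwards, by an amount the protocol does not determine

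*Protocol*

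**What the plan says.** The protocol describes the control group in several places, and not in the same way.

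- **Research question 1 (section 4):** factors are to be examined "as compared to children presenting with other acute conditions in the 12 months before diagnosis".
- **Sections 8 and 14:** "a cohort of controls presenting to their GP with acute illness but who do not have T1D will be identified from SAIL", three per case.
- **Primary objective (section 5):** cases are "compared to a matched group of controls without T1D, during the 12 months preceding diagnosis". No attendance condition is stated.
- **Inclusion criteria (section 8):** "Matched controls, for those above, from the SAIL databank". Again there is no attendance condition.
- **Section 16, Main analysis:** the quality of matching is to be examined in the "case (T1D) and control (general population of children) groups".

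The index date is worded twice. In section 8 controls "will be assigned a matched date to act as the time point for consultations in the previous 12 months"; in section 14, "This cohort will be matched on the date they presented to their GP with an acute illness".

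Section 14 also gives two matching lists. One has age, gender, location, socioeconomic class, GP and another acute illness. The other has age, gender and GP practice only.

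Cases are all children in the Brecon Group Register who meet the age and date criteria. Section 14 treats their GP consultations in the preceding 12 months as something they may or may not have had.

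**The concern.** A child who never saw a GP can be a case but cannot be a control. Number of consultations is one of the factors listed in research question 1, and section 14 analyses number of GP visits along with symptoms, diagnoses, tests and treatments. Children found through an acute attendance consult more often, on average, than registered children of the same age. They also carry more infection and antibiotic codes. Those exposures are therefore raised in controls by the way controls are found, while nothing comparable is done to cases. Matching on age, gender and practice does not remove differences in consulting between children within a matched set. Conditional logistic regression does not remove them either.

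The study looks for missed opportunities before diagnosis. A real excess of visits among cases could be understated and, under some assumptions, could vanish or reverse. The section 16 label invites a reader to take the result as a comparison with children in general. The control source is fixed at data extraction, so later wording in an analysis plan cannot undo it.

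**Working it through.** **1. Who must have attended a GP?**

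| Group | Source | Attendance required |
|---|---|---|
| Cases | Disease register | No |
| Controls, research question 1 and sections 8 and 14 | Acute-illness attenders | Yes |
| Controls, primary objective and inclusion criterion | Children without T1D | Not stated |
| Controls, section 16 | General population of children | No |

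Rows 2 and 4 are different source populations. Only row 2 conditions on attendance, and it does so for controls alone.

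**2. The protocol's own inputs (section 15).** Exposure prevalence is 30% in controls, the OR is 1.5, there are 3 controls per case, alpha is two-sided 5%, power is 80%, and 322 cases are required. A matched case-control formula gives 279 cases with no within-set exposure correlation and 324 at a correlation of 0.2, so 322 is reproduced only with an unstated correlation of about 0.2. Nothing below depends on that.

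Case odds = 1.5 × 0.30/0.70 = 0.643, so case prevalence = 0.643/1.643 = 39.1%. Suppose 30% and 1.5 refer to the general population, and selection on attendance raises control prevalence to q. The observed OR is then 0.643 ÷ [q/(1−q)]:

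- q = 33%: 0.643/0.493 = 1.31
- q = 36%: 0.643/0.5625 = 1.14
- q = 39.1%: 1.00
- q = 45%: 0.643/0.818 = 0.79

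With 390 cases and an unmatched two-proportion calculation, power is 91% at q = 30%, 60% at 33% and 20% at 36%.

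**3. How far might q move?** The documents give no visit rates, so these inputs are assumptions: mean 3 visits a year, gamma-distributed rates between children with CV 0.5 to 1.0, Poisson visits, 60% of visits acute, index visit excluded, no matching. The exposure is three or more visits in the 12 months (N ≥ 3).

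Let k = 1/CV² and θ = 3/k. In all children N is negative binomial with shape k and mean 3. Two ways of choosing controls were tried:

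- *Any acute visit in the index year* (A = acute visits in that year). P(A=0) = (1+0.6θ)^(−k). Children with A=0 have gamma rates with shape k and scale θ/(1+0.6θ). Then P(N≥3 | A≥1) = [P(N≥3) − P(A=0)·P(N≥3 | A=0)] / [1 − P(A=0)].
- *A randomly drawn acute visit.* Frequent attenders are more likely to be drawn, so rates are gamma with shape k+1 and scale θ.

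Null OR = odds in all children ÷ odds in the selected controls. A true OR of 1.5 against all children appears as 1.5 × null OR.

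| CV | P(N≥3), all | Any acute visit | Null OR | 1.5 appears as | Random acute visit | Null OR | 1.5 appears as |
|---|---|---|---|---|---|---|---|
| 0.5 | 0.515 | 0.567 | 0.81 | 1.21 | 0.641 | 0.60 | 0.89 |
| 0.8 | 0.458 | 0.572 | 0.63 | 0.95 | 0.701 | 0.36 | 0.54 |
| 1.0 | 0.422 | 0.579 | 0.53 | 0.80 | 0.738 | 0.26 | 0.39 |

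Check at CV 0.8: (0.458/0.542) ÷ (0.572/0.428) = 0.845/1.336 = 0.63.

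**4. Limiting cases.** If every child has the same visit rate and the index visit is excluded, selection changes nothing and the null OR is 1. If the control's index visit is counted, P(N≥3) under the random-visit rule at CV 1.0 rises to 0.844, and the null OR is (0.422/0.578) ÷ (0.844/0.156) = 0.730/5.41 = 0.13. The protocol does not say whether that visit counts.

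**The case against.** The best defence is that the acute-illness comparator is intended. Research question 1 asks for it, and section 14 gives specificity and predictive potential as the reason. The GP's problem is to recognise T1D among sick children who attend. Against that, the general-population label is one parenthesis in a sentence about matching quality, and the primary objective and inclusion criterion can be read as merely less specific. This stands: a reader might infer that using acute attenders is itself a mistake, and the documents do not support that. What remains is that the question requires cases also to be children who presented to a GP, and no section restricts them so.

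Other parts of the defence also stand:

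- The protocol names no main exposure. Visit number is one listed factor, and section 15 is powered on a generic one.
- The two index-date wordings can be reconciled if the assigned date is the attendance date. They need clarifying but are not a proven contradiction.
- The size rests wholly on assumed visit rates. Matching would remove part of the between-child variation, and three or more visits has a prevalence of 42% to 52% here, not 30%.
- Section 15 states its 30% for the control group, so treating 1.5 as an OR against the population is an added assumption.

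**Conclusion.** The point holds in a limited form. The control group is defined as acute-illness attenders and labelled general population, and attendance is required of controls only. Measured against children without T1D in general, ORs for number of visits and for infection, antibiotic and similar codes are biased downwards whenever children differ in how often they consult.

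For three or more visits, the illustrative null OR is 0.53 to 0.81 with any-acute-visit controls, so a true 1.5 appears as about 0.8 to 1.2. It is 0.26 to 0.60 if a random acute visit is drawn, a sampling rule that the protocol does not state. There is no bias if visit rates are equal and the index visit is excluded.

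A reader might infer that the study's central result will be reversed, or that every OR is pulled down. The documents support neither. At CV 0.5 with any-acute-visit controls a true 1.5 still shows as an excess, and symptom codes specific to T1D need not be biased in this way. The direction is well founded for the exposures named; the size, and whether an association crosses 1, are not known.

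**What to change.** Change the extraction specification before the SAIL data are cut.

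1. **Primary objective, consultation counts against children without T1D.** Sample controls from T1D-free children registered at the case's practice on the case's diagnosis date, matched on age and gender. Use that date as the index date, with no attendance condition.
2. **Research question 1.** Keep the acute-illness controls. Restrict this comparison to cases with a GP presentation, tie the control's index visit to the case's calendar time, and exclude the index visit in both groups.
3. **Wording.** Make sections 8, 14 and 16 agree on control source, index date and matching variables, which includes settling the two lists in section 14. Remove the general-population label wherever acute-illness controls are used.

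The cost is a second control extract and some added analysis on routinely held data, with no patient contact.

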In a qualitative study, Usher-Smith explored the pathway to diagnosis with families and GPs and identified that the greatest delay to diagnosis in the appraisal interval was attributable to parents (4). Most children in this relatively small study were diagnosed at their first GP encounter but in most cases, parents had already made or suspected the diagnosis themselves. However, the small sample size and retrospective recall of events limit interpretation of these results.

By investigating a large cohort of children, a more detailed understanding of the typical pathway to diagnosis can be formed including identification of opportunities for an earlier diagnosis. This study will link the Brecon Group Register, which contains diagnostic details including date of presentation of 98% of all known cases of T1D in Wales, with GP records held within the Secure Anonymised Information Linkage (SAIL) Databank. SAIL holds extensive Welsh population data, including primary,

secondary and social care data. It provides detailed clinical and demographic anonymised information on patients, including symptoms, diagnoses, prescriptions and medical history. This wealth of data makes it easier and more cost-effective to study much larger numbers of individuals over longer periods of time than is possible using traditional methods using prospectively collected data that are uninfluenced by recall bias. By analysing patients' consultations, recorded in SAIL, over the 12 months before diagnosis of T1D, a more detailed account of the prodrome of T1D in childhood will be developed.

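### Section 15's two power figures do not fit one method: on the basis that gives 322 cases, 390 cases at 3:1 give about 87% power, and the fixed ratio is unjustified if linked cases stay near 400

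*Protocol*

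**What the plan says.** Sections 3, 6, 8 and 14 set three controls per case; section 14 says they "will be identified from SAIL at the ratio of 3:1", matched on age, gender and GP practice. No reason is given for stopping at three. Section 14 also gives the purpose of the controls: "to explore the specificity and predictive potential of variables related to development of T1D". Section 10 says that the study uses routinely collected data and recruits nobody, and section 4 says that SAIL "makes it easier and more cost-effective to study much larger numbers of individuals".

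Section 15 assumes an odds ratio of 1.5 and "a moderately low prevalence rate of the risk factor 30% in the control group". It concludes: "matching 3 controls per case and using a two sided 5% alpha and 80% power, we will require 322 children with T1D". It then says that around 390 children diagnosed between 2010 and 2012 would bring power above 90%. No correlation of exposure within matched sets is stated.

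The case number differs by place. The synopsis and study summary say about 400, and the power text says about 390. Sections 8 and 14 expect about 3500 diagnoses over 2000 to 2015, which is the window in the inclusion criteria.

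**The concern.** Moving from 322 to 390 cases is a 21% increase (390/322 = 1.21). With everything else unchanged, 90% power needs about 34% more cases than 80% power (432/322 = 1.34). The claim for 390 therefore looks too high beside the claim for 322.

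The fixed ratio bears on this because more controls could make up the difference without any more cases. The usual reason for a low ratio, the cost of recruiting controls, does not apply to records already held in a databank. At stake is whether the stated power is true at the size section 15 describes, and how precisely the study can estimate odds ratios for symptoms that are rare in children without diabetes.

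**Working it through.** **Inputs from section 15.** Odds ratio ψ = 1.5; exposure in controls p0 = 0.30; M = 3 controls per case; two-sided 5% alpha; 80% power; 322 and 390 cases.

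**Assumed.** Exposure correlation φ between a case and its matched controls. It is not stated; 0.2 is used because it reproduces 322, and a range is shown.

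**Step 1: reproduce 322.** Exposure in cases is p1 = 1.5 × 0.30 / (1 + 0.30 × 0.5) = 0.391. In Dupont's matched formula, the probability that a control is exposed depends on its case:

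- r = φ√(p1·q1·p0·q0) = 0.2 × √(0.391 × 0.609 × 0.30 × 0.70) = 0.0447
- case exposed: 0.30 + 0.0447/0.391 = 0.414
- case unexposed: 0.30 − 0.0447/0.609 = 0.227

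Let e and v be the mean and variance per matched set of the number of exposed cases, given the total exposed in the set. For M = 3, e = 0.2950 and v = 0.1444 under the null; e = 0.3546 and v = 0.1485 under ψ = 1.5. Then

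n = (0.842√0.1485 + 1.960√0.1444)² / (0.3546 − 0.2950)² = 321.4, so **322**.

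Unmatched calculations do not give 322: two proportions 280, with continuity correction 294, unpooled variance 291, log odds ratio 277.

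**Step 2: power at 390 on the same basis.** Φ[(√390 × 0.0596 − 1.960√0.1444)/√0.1485] = **86.9%**. At 400 cases it is 87.7%. For 90% power, n = 431.5, so **432** cases.

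**Step 3: a check without that formula.** Scaling 80% power at 322 cases up to 390 gives Φ(2.80 × √(390/322) − 1.96) = Φ(1.12) = 86.9%.

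**Step 4: dependence on φ at 3:1.**

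| φ | cases for 80% | power at 390 |
|---|---|---|
| 0 | 279 | 91.1% |
| 0.05 | 288 | 90.3% |
| 0.1 | 298 | 89.3% |
| 0.2 | 322 | 86.9% |
| 0.3 | 355 | 83.6% |

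No row contains both 322 and a power above 90%.

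**Step 5: effect of the ratio (φ = 0.2).**

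| controls per case | power at 390 | cases for 90% |
|---|---|---|
| 3 | 86.9% | 432 |
| 4 | 89.5% | 397 |
| 5 | 91.0% | 376 |
| 10 | 93.8% | 334 |

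With 3500 cases, power is near 100% at every ratio. The 432 cases needed for 90% at 3:1 are 12% of 3500.

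**Step 6: symptoms rare in controls.** The documents give no prevalence for these. Assume 5% of cases and 0.1% to 1% of controls are exposed. With the unmatched approximation Var(log OR) = 1/a + 1/b + 1/c + 1/d, the 95% interval is the odds ratio multiplied or divided by exp(1.96√Var). For example, 390 cases at 3:1 and 0.1% give 1/19.5 + 1/370.5 + 1/1.17 + 1/1168.83 = 0.91, a factor of 6.5.

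| cases | control prevalence | exposed controls, 3:1 → 10:1 | interval factor, 3:1 → 10:1 |
|---|---|---|---|
| 390 | 0.1% | 1.2 → 3.9 | 6.5 → 3.0 |
| 390 | 0.5% | 5.9 → 19.5 | 2.5 → 1.9 |
| 390 | 1% | 11.7 → 39 | 2.1 → 1.7 |
| 3500 | 0.1% | 10.5 → 35 | 1.9 → 1.4 |

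At 390 cases and 0.1%, the chance of no exposed control is exp(−1.17) = 31% at 3:1 and exp(−3.9) = 2% at 10:1.

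**The case against.** The strongest reply is that 390 is the wrong case number. The eligibility rules cover 2000 to 2015, and with about 3500 children the power question disappears at any ratio. That is correct if most of them link. But the synopsis, summary and power text still plan for 390 to 400, and the protocol does not say which number governs.

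A second reply is that three controls per case is conventional, and that power above 90% at 390 does reproduce at 3:1 without correlation (91.1%). That also stands, but the 322 then fails. It shows that a reader who concludes that the 3:1 ratio costs the study its 90% power would be going too far: the fault is an inconsistent pair of figures, and a higher ratio is one remedy, not the cause.

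A reader might also infer that 3:1 leaves symptoms specific to diabetes with almost no exposed controls. The documents do not support this, because they give no such prevalence. It holds only near 0.1% combined with about 390 cases. Section 14 also plans to group symptoms, which would raise the prevalences analysed. A zero cell would not erase the signal, since exact or penalised methods give a finite lower bound, and such handling may sit in an analysis plan not shown here.

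Finally, feasibility is unproven. Controls must match on age, gender and practice and have an acute-illness visit that supplies the index date. The number of such children per practice is not given.

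**Conclusion.** The point holds in a limited form. The figures of 322 cases for 80% power and above 90% at 390 cannot both be right under one method. On the basis that reproduces 322, power at 390 is about 87%, some 3 percentage points below 90%. The 0.2 correlation is inferred, but the scaling check in step 3 does not depend on it.

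The fixed ratio is a secondary matter. It is unexplained, and at about 390 to 400 cases raising it to 5:1 restores 90%. With most of 3500 cases linked, it makes no practical difference to the planned OR of 1.5 at 30% exposure. The gain in precision for rare symptoms rests on the assumed prevalences and is large only for very rare symptoms in a small study.

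**What to change.** In section 15, state the exposure correlation assumed, and restate power at 390 cases and 3:1 as about 87% if 322 is kept. Reconcile the case number across the synopsis, section 3, sections 8 and 14, and section 15, and give power at the number expected to link. This costs wording only.

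If that number is near 400, replace the fixed 3:1 in sections 3, 6, 8, 14 and 15 with a variable ratio of about five controls per case where close matches exist, and report power at the ratio achieved. The planned conditional logistic regression handles sets of unequal size. The cost is a changed extract specification; some practices may not supply enough close matches, so availability should be checked with the SAIL analyst before extraction. If most of the 3500 link, 3:1 can stay with one sentence of justification.

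### The two power figures in the sample size paragraph cannot both hold: if 322 cases give 80% power, 390 cases give about 87%, not over 90%

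*Protocol*

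**What the plan says.** The Sample size paragraph of Section 15 powers the study for the case-control comparison. Its inputs are:

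- effect size: "Assuming a medium effect size (OR=1.5";
- exposure: "a moderately low prevalence rate of the risk factor 30% in the control group";
- design: "matching 3 controls per case";
- result: "using a two sided 5% alpha and 80% power, we will require 322 children with T1D".

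The next sentence gives the power at the expected number of cases: "If a total of around 390 children diagnosed with T1D were identified between 2010 and 2012 this would give the study over 90% power".

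No formula, software or case-control exposure correlation is given. Section 16 (Main analysis) plans the matched comparison "using a conditional logistic regression model to account for the non-independent observation created by matching".

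The size of the study is described in different ways. The Synopsis and the Study summary give about 400 children. Sections 8 and 14 take all diagnoses from 2000 to 2015 and expect approximately 3500.

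**The concern.** Going from 322 to 390 cases is an increase of 21% (390/322 = 1.211). With everything else fixed, that is too little to lift power from 80% to above 90%. At least one of the two figures must therefore be wrong, or they rest on different unstated assumptions.

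This is the only power statement for the primary objective. If 322 is the sound figure, the type II error at 390 cases is about 13%, where the text implies less than 10%. If the higher power is the sound figure, the stated requirement of 322 is too large by some 35 to 40 cases.

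**Working it through.** **Inputs, all from Section 15.** Odds ratio 1.5; control exposure p0 = 0.30; M = 3 controls per case; two-sided 5%, so z = 1.960. Case exposure follows as p1 = 1.5 × 0.30 / (0.70 + 0.45) = 0.3913. The exposure correlation φ between a case and its matched controls is not given, so it is treated as an assumption and varied from 0 to 0.3.

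**Step 1: reproduce 322.** The Dupont formula for matched case-control sets is

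n = (z_β √v_ψ + 1.960 √v_1)² / (e_ψ − e_1)²,

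where e and v are the mean and variance per set of the case-exposed indicator, under the odds ratio (ψ) and under no effect (1). With φ = 0.2:

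- √(p1 q1 p0 q0) = 0.2237. Control exposure is 0.30 + 0.2 × 0.2237/0.3913 = 0.4143 when the case is exposed, and 0.30 − 0.2 × 0.2237/0.6087 = 0.2265 when it is not.
- The probabilities of 1, 2 and 3 exposed members in a set of four are 0.3261, 0.2393 and 0.1251.
- These give e_ψ − e_1 = 0.05963, √v_1 = 0.3800 and √v_ψ = 0.3854.
- 80% power: n = (0.8416 × 0.3854 + 1.960 × 0.3800)² / 0.05963² = 321.4, rounded up to 322. This is the stated figure.

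**Step 2: same formula, 390 cases.** Power = Φ((√390 × 0.05963 − 1.960 × 0.3800) / 0.3854) = Φ(1.123) = 86.9%. For 90%, n = (1.2816 × 0.3854 + 1.960 × 0.3800)² / 0.05963² = 431.5, so 432 cases. At 400 cases the power is 87.7%.

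**Step 3: check that does not use φ.** Under the usual normal approximation the standardised effect grows with √n. Anchoring on 80% at 322:

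- power at 390 = Φ(2.8016 × √(390/322) − 1.960) = Φ(1.123) = 86.9%;
- cases for 90% = 322 × (3.2415/2.8016)² = 431.1, so 432. That is about 34% more than 322.

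**Step 4: can any basis give both figures?**

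| Basis | Cases for 80% | Power at 322 | Power at 390 | Cases for 90% |
|---|---|---|---|---|
| Matched, φ = 0 | 279 | 85.2% | 91.1% | 375 |
| Matched, φ = 0.05 | 288 | 84.2% | 90.3% | 387 |
| Matched, φ = 0.10 | 298 | 83.0% | 89.3% | 400 |
| Matched, φ = 0.15 | 309 | 81.6% | 88.2% | 415 |
| Matched, φ = 0.20 | 322 | 80.1% | 86.9% | 432 |
| Matched, φ = 0.30 | 355 | 76.2% | 83.6% | 475 |
| Unmatched 3:1 | 280 | 85.2% | 91.0% | 376 |
| Unmatched, continuity correction | 294 | 83.6% | 89.99% | 391 |

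No row has 322 in the first column together with more than 90% at 390. Each row that passes 90% at 390 needs no more than 288 cases for 80%.

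**The case against.** Three objections deserve weight.

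*The protocol does not show which figure is wrong.* This stands. The correlation of 0.2 was found by matching 322; the protocol does not state it. If the sponsor worked with a correlation near zero, the higher power is right and 322 is a cautious overstatement. The 87% and the 432 therefore hold only with 322 as the anchor.

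*The cause is unknown.* This also stands. A reader might infer that the authors mixed a matched and an unmatched formula, and that power above 90% appears only when matching is ignored. The documents do not support that. The matched formula itself gives 91.1% at a correlation of 0 and 90.3% at 0.05. Two different correlations, or a drafting slip, would explain the text equally well.

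*The consequence is small.* This stands in large part. The target is 80%, and 390 exceeds 322. The sample is whatever the register and the linkage supply, so no recruitment target depends on the figure. With approximately 3500 cases expected for 2000–2015, 432 is about 12% (432/3500), so power would exceed 90% unless linkage loss were very heavy; the linkage rate is not given. However, the Synopsis and the Study summary still plan for about 400, and the power sentence is tied to 390. None of this makes the two sentences agree.

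**Conclusion.** The point holds as a minor arithmetic inconsistency. With 322 cases for 80% power, 390 cases give about 87%, and 90% needs about 432. These results assume only that 322 is the right anchor and that the stated odds ratio, exposure, matching ratio and two-sided level apply to both sentences. Keeping 322 is the more natural choice, because a matched calculation fits the matched design and the planned conditional logistic regression. That is a judgement about plausibility and does not prove where the slip lies.

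A reader might go further and infer that the study is underpowered. The documents do not support that. At 390 cases the 80% target is met on either reading of the paragraph, and in every row of the table, down to 83.6% at a correlation of 0.3. The cohort defined by the inclusion criteria is also expected to be far larger than 390.

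**What to change.** Rewrite the Sample size paragraph on a single basis:

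- State the formula and the assumed exposure correlation. The sponsor should confirm the value actually used; 0.2 should not be written in merely because it reproduces 322.
- If 322 is kept, say that around 390 cases would give about 87% power and that 90% would need about 432. If the higher power is kept, replace 322 with the requirement from the same calculation (about 279 to 288 for a matched formula with correlation 0.05 or less, 280 for the unmatched formula).
- Restate the power for the 2000–2015 cohort, starting from approximately 3500 and showing a range of linkage rates, and reconcile it with the figure of about 400 in the Synopsis and Study summary and with the 2010–2012 window.

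The cost is one short recalculation and a reworded paragraph, with matching edits to the Synopsis and Study summary. Design, data extraction and analysis do not change.
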